3.3 Sample size

Sample size and power

Our sample size of 360 patients was based on identifying a 1.0 point mean difference[13] between the Cycling and Routine groups for the Physical Function Test for ICU-scored (PFIT-s) measured at 3 days after ICU discharge.[14, 15] Psychometric studies of the PFIT-s identified the minimal clinically important difference was 1.0 points.[14, 16] Logistic regression analysis of patients enrolled in TryCYCLE [7] and the CYCLE pilot randomized study [8] identified that each 1.0 point increase in PFIT-s at ICU discharge (representing better function) was associated with a 40% reduction in the composite outcome of death, readmission to ICU, or requiring paid assistance for activities of daily living at hospital discharge.[13] Based on a standard deviation of 2.5 points at ICU discharge,[7, 17] a 1.0 point difference between groups,[13, 14, 16] and 90% power (0.05 alpha), we need to randomize and analyze 266 patients (133 per group). Based on 66 patients enrolled in the CYCLE Pilot RCT, we anticipated approximately 35% total attrition (25% ICU mortality, 1% mortality in the first 3 days post-ICU discharge, 5% missed primary outcome assessments at 3 days post-ICU, and 5% unblinded). Therefore, we will recruit 360 patients overall.

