5.5 Baseline patient characteristics

We will summarize categorical data as counts and percentages. We will summarize continuous data as means, standard deviations, or median and interquartile range, if data are non-normally distributed. We will not conduct tests of statistical significance between randomized groups; rather, we will note the clinical importance of any imbalance between groups.

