For each continuous secondary outcome, we will conduct a linear regression. We will conduct secondary outcome analyses adjusting for age (≥ 65 years versus <65 years) only. To avoid the risk of overfitting in our analyses, we will not adjust for center when analysing our secondary outcomes. We will report the results of the linear regressions as mean differences with corresponding 95% CIs. If needed to normalize the data, we will perform the linear regression on the log-transformed outcome. If the data are still skewed, we will perform nonparametric analyses. Because secondary analyses are underpowered and hypothesis-generating, we will not present p-values. In the Supplementary appendix, we describe the scoring algorithm to account for incomplete data in the 30 Second Sit to Stand and 2-minute walk tests based on a patient’s observed function.

Time to ICU, hospital, and 90-day mortality will be analyzed using Cox proportional hazards regression analysis. We will report hazard ratios (HRs) and corresponding 95% CIs. All other binary outcomes will be analyzed using logistic regression analysis, reporting odds ratios (ORs) with corresponding 95% CIs. We will check the assumptions of the different regression analyses by examining residuals and using other relevant methods. Table 3 describes secondary outcomes analyses. Analysis of Harms is described in Section 6.5.

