6.4 Additional analyses

Subgroup analyses

We will perform three exploratory *a priori* subgroup analyses to investigate potential treatment effect modification for the primary outcome. All subgroup analyses will be adjusted for age and center.

- i. Age ≥ 65 versus < 65 years.
- ii. Baseline Clinical Frailty ≥ 5 versus < 5 .
- iii. Male versus female.

In separate linear regression models for each of the three subgroup analyses, we will include randomized treatment allocation, the subgroup variable, and the interaction between the subgroup variable and randomized treatment allocation as independent variables. These analyses will be adjusted for age and center. We hypothesize that the treatment effect will be greater for older compared to younger patients [45], greater in patients with frailty compared to those without [45], and greater in males compared to females [46, 47]. For statistical significance in the subgroup analyses, we will use an alpha of 0.10 for the interaction term. We will assess the credibility of any statistically significant subgroup effect using the method of Schandelmaier *et al.*[48] We will report these data in a forest plot.

Sensitivity analyses

To assess the robustness of our findings, we will conduct five sensitivity analyses for our primary outcome. All sensitivity analyses will be adjusted for age and center, unless specified.

- i. To account for ICU mortality on the primary outcome, we will conduct an analysis where we include all patients who died prior to 3-days post-ICU discharge and will assign a PFIT-s score of 0 for those patients.
- ii. We will conduct a linear regression analysis that includes only PFIT-s assessments performed by assessors blinded to treatment allocation.
- iii. We will conduct an analysis where we only include patients with adherence to the protocol on $\geq 80\%$ of planned ICU days. Adherence is defined as either received the randomized intervention or had a temporary exemption.
- iv. We will investigate the effect of missing data by conducting a complete case analysis, including only those patients with a total PFIT-s score at 3 days post ICU discharge.
- v. To determine if the cycling effect is affected by centre, we will conduct analysis adjusting for age only.

See Table 2 for further details.

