Katz Activities of Daily Living scale [38]	The patient's ability to complete 6 tasks: bathing, dressing, toileting, feeding, continence, and bed mobility. A rater assesses whether the patient is dependent or independent according to pre-specified criteria. Total scores range from 0 to 6,	ICU discharge, hospital discharge	Includes survivors at each time point. Separate linear regressions for each timepoint, adjusted for age

Outcome	Description of Outcome	Measurement Timing	Analysis
	with higher scores representing better function.		
Clinical Frailty Scale [37]	Frailty includes a reduction in physical reserve and loss of function across multiple body systems. The clinical frailty scale is a 9-point scale, with higher scores representing more frailty.	Hospital discharge, 90 days post-randomization	Includes survivors at each time point. Separate linear regressions for each timepoint, adjusted for age
ICU Length of Stay	Days in ICU	ICU discharge	Linear regression, adjusted for age
Hospital Length of Stay	Days in hospital	Hospital discharge	Linear regression, adjusted for age
Mortality	Death	ICU discharge, hospital discharge, 90 days post-randomization	Separate Cox proportional hazards models for each timepoint, adjusted for age
Hospital Discharge Location	Same or better living location at hospital discharge from baseline	Hospital discharge	Includes survivors. Logistic regression, adjusted for age

Table 4: PFIT-s Scoring (adapted from Denehy et al.)[14]

	PFIT-s Component value score			
	0	1	2	3
Shoulder strength	MRC grade 0, 1, or 2	MRC grade 3	MRC grade 4	MRC grade 5
Knee Strength	MRC grade 0, 1, or 2	MRC grade 3	MRC grade 4	MRC grade 5
Sit-to-Stand assistance	Unable	Assist of 2 people	Assist of 1 person	No assistance
Step Cadence	Unable	>0 to 49	50 to <80	>80

MRC = Medical Research Council strength grade (0 to 5)

Supplement Table 1: Summary of Assessments

	Study Period							
	Enrolment	Allocation	Post-allocation					
Timepoint	ICU admission	0	In ICU	ICU awakening	ICU D/C	3 days post-ICU D/C	Hospital D/C	90 days post-randomization
Enrolment:								
Eligibility screening	X							
Informed consent	X							
Allocation		X						
Interventions:								
In-bed cycling + routine PT			X	X	X			
Routine PT			X	X	X			
Assessments:								
Severity of illness: APACHE II [53]	X							
Charlson Comorbidity Index[54]	X							
Functional Comorbidity Index[55]	X							
Clinical Frailty Scale [37]	X						X	X
Function: Katz Activities of Daily Living scale[38]	X				X		X	

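### Katz and Clinical Frailty Scale scores are taken at ICU admission, but their follow-up models adjust for age group only and leave the baseline score unused

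*SAP*

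**What the plan says.** Supplement Table 1 marks the Clinical Frailty Scale at ICU admission, hospital discharge and 90 days. It marks Katz at ICU admission, ICU discharge and hospital discharge. No other scale in Table 3 has an admission value; the rest begin at ICU awakening or later.

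The analysis given in Table 3 for both scales is "Includes survivors at each time point. Separate linear regressions for each timepoint, adjusted for age". Section 6.2 sets the same rule for all continuous secondary outcomes: "We will conduct secondary outcome analyses adjusting for age (≥ 65 years versus <65 years) only". The reason that follows is "To avoid the risk of overfitting in our analyses, we will not adjust for center when analysing our secondary outcomes".

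Baseline frailty appears in one other place, section 6.4, as a subgroup variable for the primary outcome: "Baseline Clinical Frailty ≥ 5 versus < 5". Baseline Katz enters no model. For baseline differences in general, section 5.5 says only that "we will note the clinical importance of any imbalance between groups". No change score, analysis of covariance or baseline-adjusted sensitivity analysis is planned for either scale.

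**The concern.** A patient's score on a scale at admission is the obvious candidate predictor of the score on that scale later. The trial collects it for these two scales and then compares follow-up means without it. Two things are lost. The confidence interval is wider than the data allow. And if the arms happen to differ in frailty or function at admission, part of that difference appears as a treatment effect. Randomization was stratified by center and age (section 3.2), so nothing in the design balances either score.

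The reason given for a short covariate list does not reach this case. Center adds many terms in a multi-center trial, whereas a baseline score adds one.

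Interval width matters here because the SAP states "Because secondary analyses are underpowered and hypothesis-generating, we will not present p-values". Readers will have only the estimates and intervals. The 90-day CFS comparison is also smaller, since section 6.1 limits 90-day outcomes to patients enrolled after March 7, 2018.

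**Working it through.** **Inputs.** The planned models come from section 6.2 and Table 3, and the baseline schedule from Supplement Table 1. The SAP gives no sample size, SD or baseline-to-follow-up correlation for Katz or CFS. I use 133 per arm, the number for the primary outcome in section 3.3, for illustration only. The correlation r is assumed and shown as a range. Because age group is already in the model, r means the correlation within age group.

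**The plan's own figure.** Section 3.3 gives 266 patients (133 per group) for a difference of 1.0, SD 2.5, 90% power and two-sided 5%. The normal approximation is n per arm = 2 × (1.96 + 1.2816)² × 2.5² / 1.0² = 131.3, so 132, or 264 in total. The exact t test has 89.9% power at 132 per arm and 90.1% at 133, so 266 is reproduced.

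**Precision.** Adding the baseline score multiplies the variance of the treatment estimate by 1 − r². The standard error is multiplied by √(1 − r²), and the equivalent increase in sample size is 1/(1 − r²) − 1.

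| r (assumed) | Variance ratio | SE ratio | SE reduction | Equivalent extra patients |
|---|---|---|---|---|
| 0.1 | 0.99 | 0.995 | 0.5% | 1% |
| 0.2 | 0.96 | 0.980 | 2% | 4% |
| 0.3 | 0.91 | 0.954 | 5% | 10% |
| 0.5 | 0.75 | 0.866 | 13% | 33% |
| 0.6 | 0.64 | 0.800 | 20% | 56% |
| 0.7 | 0.51 | 0.714 | 29% | 96% |

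**Chance imbalance.** With 133 per arm, the difference in baseline means has a standard error of √(2/133) = 0.123 SD, so its 95% range is about ±1.96 × 0.123 = ±0.24 SD. A fraction r of the realized difference carries into the age-only estimate. A 0.2 SD baseline difference shifts it by 0.2 × r, which is 0.06, 0.10 and 0.14 SD at r = 0.3, 0.5 and 0.7.

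**Simulation check.** I ran 4,000 trials with 133 per arm and no treatment effect at each of three values of r. For simplicity age was left out of both models.

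| r | SE ratio, simulated | SE ratio, theory | Slope of unadjusted estimate on baseline difference | Correlation of adjusted estimate with baseline difference |
|---|---|---|---|---|
| 0.3 | 0.956 | 0.954 | 0.29 | −0.01 |
| 0.5 | 0.859 | 0.866 | 0.52 | 0.02 |
| 0.7 | 0.723 | 0.714 | 0.69 | −0.02 |

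Both estimators averaged about zero, so neither is biased over repeated randomization. The unadjusted one moves with the baseline difference and the adjusted one does not.

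**The case against.** The plan contains no contradiction. Section 6.2 and Table 3 agree, the model is fully specified, and regression on arm and age group is valid under randomization. The outcomes are declared exploratory, and section 5.5 at least ensures that an imbalance would be visible. This stands: it is a loss of efficiency, not an error that biases the result on average.

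The size depends wholly on r. At r = 0.2 the gain is worth only 4% more patients, and whatever age group already explains does not count. This also stands, and it is why r is defined within age group and shown as a range.

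The case is weaker for Katz. Patients had to walk independently before admission and severe prior cognitive impairment was excluded (Table 1), so a 0 to 6 score may sit near its ceiling. The SAP does not say whether the admission Katz describes the state before illness or the state at admission; the latter might sit near the floor in ventilated patients. Either would shrink the gain. For CFS, a planned split at 5 implies that spread at baseline is expected.

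Restriction to survivors should not be given much weight. It reduces numbers and so somewhat increases chance imbalance. Systematic imbalance would require treatment to affect who survives, and one covariate would not remove that.

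Finally, section 6.2 allows log transformation and then nonparametric methods if data stay skewed. The 1 − r² result describes the linear model, so a full remedy must also cover that fallback and missing admission scores. None of these points gives a reason to leave the baseline score out.

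**Conclusion.** The concern holds. In four models (Katz at ICU and hospital discharge, CFS at hospital discharge and 90 days) the plan leaves out a baseline measure of the outcome that the trial already collects, and its overfitting argument does not cover that omission. The cost is intervals wider by a factor of 1/√(1 − r²) and estimates that shift by r times any chance baseline difference. At assumed r of 0.3 to 0.6, adjustment would cut the standard error by 5% to 20%. The gain is probably more secure for CFS than for Katz. If r is near zero almost nothing is gained, and only a degree of freedom is spent. The omission adds no bias on average and does not touch the primary analysis. The change is worth making because it is cheap, and because settling it before analysis avoids a post hoc decision if an imbalance appears.

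**What to change.** In section 6.2 and the two Table 3 rows, state that both CFS models include the ICU-admission CFS score, and both Katz models the ICU-admission Katz score, as a covariate alongside age group. Limit the overfitting sentence explicitly to center. Add a clause on how a missing admission score is handled, and another on how the baseline score enters if the nonparametric fallback is used. State also whether the admission Katz refers to status before the illness or at admission.

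The cost is a few lines of SAP text, one extra term and one degree of freedom in each of four models, and no new data.

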6.2 Analysis methods

Statistical analysis

We will analyze patients according to the group to which they were randomized for all outcomes and will use multiple imputation to handle missing data (see section 6.3). We will summarize

baseline characteristics by group reported as mean (SD) or median (first quartile, third quartile) for continuous variables and count (percent) for categorical variables. The criterion for statistical significance will be set at $\alpha=0.05$ for the Primary Outcome. P-values will be reported to 3 decimal places, with those less than 0.001 reported as $p<0.001$.

Analysis of the Primary outcome

To determine if there is a difference in PFIT-s score at 3 days after ICU discharge between the Cycling and Routine groups, we will conduct a linear regression, including randomization (Cycling vs. Routine) as an independent variable. We will adjust for age (≥ 65 years versus <65 years) and clinical site as these were used as stratification variables in the randomization. We will report the results of the regression as mean difference in PFIT-s with corresponding 95% confidence intervals (CIs) and p-values. We consider a 1-point difference in score clinically important.[14, 16] Although the goal was to have all outcome assessors remain blinded to treatment allocation, this was not always feasible. To maximize use of available data, we will include all PFIT-s measures at 3 days post-randomization, regardless of blinding status of the outcomes assessor and report the proportion of assessments performed by blinded assessors.

To account for incomplete component data in the PFIT-s at 3 days post-ICU, we will concurrently consider data from the PFIT-s, 30s sit-to-stand, and 2-minute walk tests. We will evaluate all PFIT-s data components at 3-days post-ICU. We will identify all patients with any incomplete physical function data and review the scored values for all 4 components of the PFIT-s (i.e., shoulder flexion, knee extension, level of assistance required for the sit-to-stand, and step cadence). In the PFIT-s, a score of “0” represents a lack of physical ability to complete the outcome measure. Thus, if a patient attempted the item and was unsuccessful, the item receives a score of “0”, which is a true 0 (Table 4). See supplementary appendix for further details. Table 2 describes the primary outcome analysis.

Analysis of Secondary outcomes

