Patient-reported functional scale for the ICU [56]					X		X	X
Physical Strength and Function:				X	X	X (blinded)	X (blinded)	
Physical Function ICU Test (scored)[14, 15]				X	X	X (blinded, Primary)	X (blinded)	
Medical Research Council Sum Score[49]				X	X	X (blinded)	X (blinded)	
30-second sit to stand[26]				X	X	X (blinded)	X (blinded)	

CYCLE Statistical Analysis Plan

	Study Period							
	Enrolment	Allocation	Post-allocation					
Timepoint	ICU admission	0	In ICU	ICU awakening	ICU D/C	3 days post-ICU D/C	Hospital D/C	90 days post-randomization
2-minute walk test[28]					X	X (blinded)	X (blinded)	
Psychological distress: Intensive Care Psychological Assessment Tool [31]				X				
Health-related Quality of Life: Euro-QOL 5D-5L[33, 34]					X		X	X
Hospital Anxiety and Depression Scale [36]								X
Data Collection:								
Baseline demographics	X							
Co-interventions			Document daily on CRFs					
Study-related Serious Adverse and Adverse Events			Document daily on CRFs					
Duration of mechanical ventilation								
ICU and Hospital Length of Stay							X	
Mortality					X		X	X

Supplement 2: Scoring algorithm for incomplete data in the PFIT-s

To account for incomplete component data in the PFIT-s, we will concurrently consider data from the PFIT-s, 30s sit-to-stand, and 2-minute walk tests at 3 days post-ICU or relevant time point (i.e., ICU awakening, ICU discharge, hospital discharge). For each patient with incomplete PFIT-s component data, we will evaluate the item within the context of the other scored PFIT-s items. For example, if a patient had a knee strength PFIT-s score of 1 or less (reflecting a Medical Research Council score of 3 or less and representing an inability to complete movement against gravity with any resistance), and had incomplete data for the sit-to-stand assistance component, then we would code sit to stand a score of 0, as this patient would likely not have the strength to stand. Likewise, if a patient completed the sit-to-stand component, needed assistance from 2 or more people, and data for step cadence were incomplete, we would assign step cadence a score of 0, as this patient would likely not have the strength to take any steps. In contrast, if a patient required 1 person to stand, and data for step cadence were incomplete, we would code this as missing data, as we do not have enough information to assess this patient's ability to perform the assessment.

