To reduce bias, two research personnel will be blinded to the patient's randomized allocation and clinical site. The research personnel will only evaluate patients with incomplete data. We will document the rationale for all decisions in the study analytic data set. The two research personnel will aim for consensus, however if there is disagreement, we will invite a third clinical research coordinator to make a final judgement. We will use the following scoring algorithm based on a patient's observed function (Table S2):

Table S2: PFIT-s scoring algorithm

		PFIT-s Component value scored if incomplete			
	Observed	Shoulder strength	Knee strength	Sit-to-Stand Assistance	Step Cadence
PFIT-s Components:					
Shoulder strength	Any	N/A	Missing	Missing	Missing
Knee Strength	0 (MRC grade 0, 1, or 2)	Missing	N/A	0 (unable)	0 (unable)
	1 (MRC grade 3)	Missing	N/A	0 (unable)	0 (unable)
	2 (MRC grade 4)	Missing	N/A	Missing	Missing
	3 (MRC grade 5)	Missing	N/A	Missing	Missing
Sit-to-Stand assistance	0 (unable)	Missing	Missing	N/A	0 (unable)
	1 (assist of 2 people)	Missing	Missing	N/A	0 (unable)
	2 (assist of 1 person)	Missing	Missing	N/A	Missing
	3 (no assistance)	Missing	Missing	N/A	Missing
Step Cadence	Unable	Missing	Missing	Missing	N/A
	Able to clear their foot more than once	Missing	Missing	Missing	N/A

		PFIT-s Component value scored if incomplete			
	Observed	Shoulder strength	Knee strength	Sit-to-Stand Assistance	Step Cadence
Other Performance-based outcomes:					
30s Sit to Stand	1 or more repetitions; assistance of 2 or more people	Missing	Missing	1 (assist of 2 people)	0 (unable)
2-minute walk	Any score >0 m	Missing	Missing	Missing	Missing
	Any score >0 m and information re: assistance	Missing	Missing	Missing	Missing

N/A = not applicable; MRC = Medical Research Council strength grade (0 to 5)

Supplement 3: Scoring algorithm for incomplete data in the 30 Second Sit to Stand and 2-minute walk tests

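### Table S2 uses an observed 30-second sit-to-stand only when two or more helpers were needed, so the PFIT-s completion rules can fill in low item scores but never a 2 or 3

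*SAP*

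**What the plan says.** For incomplete PFIT-s components, section 6.2 states that "we will concurrently consider data from the PFIT-s, 30s sit-to-stand, and 2-minute walk tests". Supplement 2 repeats this for day 3 after ICU discharge and the other assessment times.

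Supplement 2 then makes Table S2 the working rule: "We will use the following scoring algorithm based on a patient's observed function (Table S2"). Two raters, blinded to arm and site, apply it to incomplete cases and record their reasons. A third person decides if they disagree.

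Table S2 has a single 30STS row, "1 or more repetitions; assistance of 2 or more people". It gives sit-to-stand 1 and step cadence 0. Both 2-minute-walk rows, including "Any score >0 m and information re: assistance", give *Missing* for all four items.

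Table 4 scores the sit-to-stand item by assistance alone: 0 for unable, 1 for two helpers, 2 for "Assist of 1 person", and 3 for no help.

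For step cadence, Supplement 2 gives a reasoned rule: "if a patient required 1 person to stand, and data for step cadence were incomplete, we would code this as missing data".

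Section 6.3 says that missing performance-based outcomes are multiply imputed. It does not say whether items or totals are imputed, or from which variables. Sensitivity analysis iv in section 6.4 keeps only patients who have a PFIT-s total.

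**The concern.** A full stand on the 30STS with one helper, or with none, shows what the sit-to-stand item measures just as directly as a stand with two helpers. The SAP gives no reason for using the two-helper observation and leaving the other two unused.

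The gap runs in one direction. Weak patients get their blank items filled and abler patients do not. Where knee strength is scored 0 or 1, the printed knee rule even records a patient who was seen to stand as unable to stand.

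This concerns the primary outcome. At stake are the completeness of the score, the level of the arm means (above all in the complete-case analysis), and a clear rule for the blinded raters.

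**Working it through.** **1. What Table S2 can fill.** All non-missing entries are listed here.

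| Observed | Sit-to-stand item if blank | Step cadence if blank |
|---|---|---|
| Knee item 0 | 0 | 0 |
| Knee item 1 | 0 | 0 |
| Sit-to-stand item 0 | – | 0 |
| Sit-to-stand item 1 | – | 0 |
| 30STS, two or more helpers | 1 | 0 |

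Every other entry is *Missing* or not applicable. Sit-to-stand can be filled with 0, 0 or 1 and cadence only with 0. No rule yields a 2 or 3.

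**2. 30STS with fewer than two helpers and a blank sit-to-stand item.**

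| Helpers on 30STS | Table 4 score for that performance | Table S2, knee 2 or 3 | Table S2, knee 0 or 1 |
|---|---|---|---|
| One | 2 | *Missing* | 0 |
| None | 3 | *Missing* | 0 |

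If the rescaling from 12 to 10 points is linear (the SAP does not give the transform), a 0 in place of 2 costs that patient 2 × 10/12 = 1.67 points, and a 0 in place of 3 costs 3 × 10/12 = 2.5 points. The two-helper row also collides with the knee rule (1 against 0), and no order of precedence is set.

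**3. Inputs for a size.** The SAP gives no figure for partly incomplete PFIT-s assessments. Section 3.3 supplies the SD of 2.5 and the difference of 1.0. They reproduce its sample size: 2 × (1.960 + 1.282)² × 2.5² / 1.0² = 131.3, so 132 per arm. The t-test version gives 132.3, so 133 per arm and 266 in all.

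**4. Illustration for the complete-case analysis.** Assumptions not in the SAP:
- The total is normal with SD 2.5, and the control mean is 5 or 6.
- A total of 4.0 or more goes with sit-to-stand 2 or 3.
- A share q of patients in each arm has the item blank but the 30STS observed.
- Blanks below 4.0 are recovered, and blanks at or above it are not.

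With z = (mean − 4)/2.5, normal density φ(z) and distribution function Φ(z), the lost share is qΦ(z) and the arm mean falls by q × 2.5 × φ(z) / (1 − qΦ(z)).

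Worked case, control mean 5 and q = 10%: z = 0.4, φ = 0.3683, Φ = 0.6554. The fall is 0.1 × 2.5 × 0.3683 / (1 − 0.0655) = 0.099. For cycling at mean 6: z = 0.8, φ = 0.2897, Φ = 0.7881, and the fall is 0.0724 / 0.9212 = 0.079. The difference becomes 1.0 + 0.099 − 0.079 = 1.020. For mean 7: z = 1.2, φ = 0.1942, Φ = 0.8849.

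| Control / cycling mean | q | Fall, control | Fall, cycling | Complete-case difference (true 1.0) |
|---|---|---|---|---|
| 5 / 6 | 5% | 0.048 | 0.038 | 1.010 |
| 5 / 6 | 10% | 0.099 | 0.079 | 1.020 |
| 5 / 6 | 20% | 0.212 | 0.172 | 1.040 |
| 6 / 7 | 5% | 0.038 | 0.025 | 1.012 |
| 6 / 7 | 10% | 0.079 | 0.053 | 1.025 |
| 6 / 7 | 20% | 0.172 | 0.118 | 1.054 |

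Simulating the same model gave falls of 0.03 to 0.21 and differences of 1.01 to 1.06. Lost totals were about 3% to 16% in control and 4% to 18% in cycling.

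With no true effect and equal q, both arms fall equally and the difference stays at 0. With unequal q it would not: at mean 5, with 10% blank in one arm and 5% in the other, the gap is 0.099 − 0.048 = 0.051.

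**The case against.** **The rule is absent, not printed.** No row says that a 30STS with one or no helper leaves the item *Missing*. The raters are told to weigh the 30STS and might code 2 or 3. This stands in part: the result follows from the other rows and the omission. But Table S2 is named as the algorithm, and its only printed answers for these patients are *Missing* or 0. If raters must improvise on the primary outcome, that is itself a reason to write the rule down. Table S2 also breaks across a page just above the 30STS row, so the PDF should be checked for a row lost in text extraction.

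**One item is observed, not the score.** A reader might infer that abler patients lose a primary score that was in effect observed. The SAP does not support this. The total also needs step cadence and both strength items, and leaving an incomplete cadence *Missing* with one helper is a reasoned choice in Supplement 2: "we would code this as missing data, as we do not have enough information to assess". New rows complete a total only when the other three items are present.

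**Patients are not lost from the primary analysis.** Missing scores are multiply imputed (6.2, 6.3), and only sensitivity analysis iv drops these patients. This stands.

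**Whole-score imputation is not stated.** A reader might infer that abler patients are pulled down to the arm average. That needs totals to be imputed without the observed items as predictors, and 6.3 is silent on this. Under assumed item models, patients with sit-to-stand 2 or 3 lie 0.8 to 2.5 points above the overall mean. With 5% affected, the arm means would shift by 0.05 × 0.8 = 0.04 to 0.05 × 2.5 = 0.125 points. These figures depend wholly on the assumed inputs.

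**Helper number may not be recorded.** The SAP does not say that it is noted with the 30STS, and repetitions alone cannot separate item 2 from item 3. This stands and limits the fix. A blank item beside a completed 30STS may also be rare.

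**Conclusion.** The gap is real. Section 6.2 and Supplement 2 promise to use the 30STS, and Table S2 does so only for patients who needed two or more helpers. For the others, following the table leaves the item blank or records it as unable, where Table 4 would give 2 or 3.

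The consequence is modest: some lost precision and a small downward pull on arm means, mainly in sensitivity analysis iv. In the illustration the pull is 0.03 to 0.21 points with 5% to 20% of items blank, and the treatment difference moves from 1.0 to at most 1.06, against a clinically important difference of 1.0. This rests on the assumed means, the cut-off and an equal blank share in both arms, and it leaves out patients scored 0 under the knee rule. The true number affected is unknown. The SAP does not support a conclusion that the primary comparison is materially biased. The change is worth making because it is cheap, follows from the SAP's own scale and concerns the primary outcome.

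**What to change.** - **Table S2:** where the number of helpers was recorded with the 30STS, add two rows. One or more repetitions with one helper gives sit-to-stand 2, and with no helper gives 3. Both leave an incomplete step cadence *Missing*, as the table already does for sit-to-stand 2 or 3. Where helper number was not recorded, say that the item stays *Missing*.
- **Precedence:** state that an observed 30STS overrides the knee-strength rule. This also settles the conflict with the existing two-helper row.
- **Section 6.3:** state that when some PFIT-s items are observed, only the missing items are imputed, with the observed items and the 30STS among the predictors, and the total is then formed.

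The cost is two table rows and a few sentences, using data already scheduled at the same assessment. The downside is a slightly more complex imputation model. Both changes should be fixed before the blinded raters begin.
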